2.4.2 Prior, concomitant and post therapies

Anti-neoplastic medications and concomitant medications will be coded using the WHO Drug Reference Listing (DRL) dictionary that employs the WHO Anatomical Therapeutic Chemical (ATC) classification system. Anti-neoplastic surgery as well as concomitant surgical and medical procedures will be coded using MedDRA. Details regarding MedDRA and WHO DRL version will be included in the footnote in the tables/listings.

Prior anti-cancer therapy

The number and percentage of subjects who received any prior anti-neoplastic medications, prior anti-neoplastic radiotherapy or prior anti-neoplastic surgery was summarized in the [\[Primary CSR\]](#) and will not be reported.

Post-treatment anti-cancer therapy

Anti-neoplastic medications since discontinuation of study treatment will be summarized by ATC class, preferred term, overall and by treatment group by means of frequency counts and percentages using the FAS. Separate listings will be produced for medications, radiotherapies, and surgeries.

Concomitant medications

Concomitant therapy is defined as all interventions (therapeutic treatments and procedures) other than the study treatment administered to a subject coinciding with the study treatment period. Concomitant therapy includes medications (other than investigational drugs) starting on or after the start date of study treatment or medications starting prior to the start date of study treatment and continuing after the start date of study treatment.

Concomitant medications will be summarized by lowest ATC class and preferred term using frequency counts and percentages. Surgical and medical procedures will be summarized by SOC and preferred term. These summaries will include:

1. Medications starting on or after the start of study treatment but no later than 30 days after start of last dose of study treatment and
2. Medications starting prior to start of study treatment and continuing after the start of study treatment.

All concomitant therapies will be listed. Any concomitant therapies starting and ending prior to the start of study treatment or starting more than 30 days after the last date of study treatment will be flagged in the listing. The safety set will be used for all concomitant medication tables and listings.

2.5 Analysis of the primary objective

2.5.1 Phase Ib

The primary objective of the study's Phase Ib part is to estimate the MTD or RP2D of EGF816 in combination with INC280 in EGFR^{L858R/ex19del} NSCLC subjects who have progressed on EGFR TKI treatment (e.g. gefitinib, erlotinib, or afatinib).

The primary objective for the Phase Ib was analyzed in the primary analysis and reported in the [\[Primary CSR\]](#). No analysis will be done for the final CSR.

2.5.2 Phase II

The primary objective of the Phase II part is to estimate the preliminary anti-tumor activity of EGF816 in combination with INC280 measured by ORR determined by the Investigators' assessment in accordance with RECIST 1.1 in each of the groups 1 to 3. In Group 4 the primary

objective is to characterize the safety and tolerability of EGF816 in combination with INC280 when taken with food.

The primary objective for the Phase II was analyzed in the primary analysis and reported in the [primary CSR]. The analyses described below will be updated including the data collected for subjects ongoing at the cutoff date for the primary analysis.

2.5.2.1 Primary endpoint – Phase II Groups 1, 2, and 3

ORR is defined as the proportion of subjects with best overall response (BOR) of complete response (CR) or partial response (PR) according to RECIST 1.1 (see [CSP Appendix 1]). ORR will be calculated based on the FAS using local investigators review of tumor assessment data. Tumor assessments performed before the start of any further antineoplastic therapy (i.e. any additional secondary antineoplastic therapy or surgery) will be considered in the assessment of BOR. Radiotherapy to the bone or central nervous system (CNS), and surgical resection of CNS metastases as well as palliative bone radiotherapy is allowed as per protocol, and will not be considered in determining antineoplastic therapy usage.

The ORR will be estimated by group or sub-group as assigned based on baseline mutation status and prior systemic antineoplastic therapy. The following groups will be considered (see also Section 1.1.2).

- Group 1, EGFRmut, any T790M, any MET, 2/4L antineoplastic, EGFR TKI resistant
- Group 2, EGFRmut, de novo T790M, any MET, 1/3L antineoplastic, EGFR TKI naïve
- Group 3, EGFRmut, T790M negative, any MET, 1L antineoplastic first line

Best overall response

BOR is the best response recorded from the start of the treatment until documented radiological disease progression/recurrence. However, any assessments taken more than 30 days after the last dose of study treatment will not be included in the best overall response derivation.

The study requires that for a partial response (PR) or complete response (CR) changes in tumor measurements must be confirmed by repeat assessments performed no less than 4 weeks after the criteria for the response are first met.

The best overall response for each subject is determined from the sequence of overall (lesion) responses according to the following rules:

- CR = at least two determinations of CR at least 4 weeks apart before the end of treatment.
- PR = at least two determinations of PR or better at least 4 weeks apart before the end of treatment (and not qualifying for a CR).
- SD = at least one SD assessment (or better) >7 weeks after start of treatment (and not qualifying for CR or PR).
- PD = progression ≤ 17 weeks after start of treatment (and not qualifying for CR, PR or SD).
- UNK = all other cases (i.e. not qualifying for confirmed CR or PR and without SD after more than 7 weeks or early progression within the first 17 weeks).

Subjects discontinuing from the study for PD must have it documented by radiologic evaluation. In cases of clinically-evident disease progression, all efforts should be made to perform a radiologic evaluation. Subjects with symptoms of rapidly progressing disease without radiologic evidence will not be classified as progression.

2.5.2.2 Statistical hypothesis, model, and method of analysis – Phase II Groups 1, 2, and 3

The Bayesian model employed for the primary analysis will not be repeated.

For the final CSR frequencies of the BOR categories will be presented and the response rate will be summarized using descriptive measures including 95% confidence intervals (CI) using the exact method [Clopper and Pearson 1934].

Individual lesion measurements and overall response at each assessment will be listed by group and subject.

2.5.2.3 Handling of missing values/censoring/discontinuations – Phase II Groups 1, 2, and 3

Subjects with unknown or missing BOR will be counted as failures. If there is no baseline tumor assessment, all post-baseline overall lesion responses are expected to be ‘Unknown’. If no valid post-baseline tumor assessments are available, the best overall response must be ‘Unknown’ unless progression is reported. For the computation of ORR, these subjects will be included in the FAS and will be counted as failures.

Censoring for new anti-cancer therapy

For BOR only tumor assessments performed before the start of any new anti-cancer therapy (including medication, radiotherapy and surgery) will be considered.

PFS will be censored at the date of the last adequate tumor assessment if no PFS event is observed prior to the analysis cut-off date or before the start of the new anti-cancer therapy date, whichever is earlier.

[figure not shown]
The protocol allows radiotherapy to the bone or central nervous system (CNS), and surgical resection of CNS metastases as well as palliative bone radiotherapy (that is, these will not lead to censoring).

Derivation of new anti-cancer therapy

To determine the use of new anti-cancer therapy, data entered in the following CRFs will be considered [REDACTED]:

- Antineoplastic Therapy Since Discontinuation of Study Treatment – Medication,
- Antineoplastic Therapy Since Discontinuation of Study Treatment – Radiotherapy,
- Antineoplastic Therapy Since Discontinuation of Study Treatment – Surgery.

In addition certain therapies entered in the CRF Prior and Concomitant Medications (domain CM) will be considered, if they were started after start of study treatment.

2.5.2.5 Primary endpoint – Phase II Group 4

Frequencies of treatment-emergent AEs will be calculated to characterize the safety and tolerability of the study treatment. The Safety Set will be used for summary tables.

2.5.2.6 Statistical hypothesis, model, and method of analysis – Phase II Group 4

Adverse events will be analyzed as described in the section on safety analysis, [Section 2.8.1](#).

2.5.2.7 Handling of missing values/censoring/discontinuations – Phase II Group 4

Summary tables for AEs will include events collected in the on-treatment period. If dates are incomplete and no clear assignment to pre-, on-, or post-treatment period can be made, then on-treatment will be assumed (see [Section 5.1.2](#)).

2.6 Analysis of the key secondary objective

No key secondary objective was defined.

2.7 Analysis of secondary efficacy objectives

The secondary efficacy objective for Phase Ib as well as Phase II is to evaluate the preliminary anti-tumor activity of EGF816 in combination with INC280.

2.7.1 Secondary endpoints

The secondary efficacy endpoints in Phase Ib and Phase II are BOR, ORR (if not already part of the primary analysis), disease control rate (DCR), duration of response (DOR), time to response (TTR), and progression-free survival (PFS). These endpoints are based on investigator assessment in accordance with RECIST 1.1. An additional endpoint is overall survival (OS).

For supportive analyses BOR, ORR, DCR, DOR, TTR, and PFS will also be evaluated based on the BIRC review of tumor data in accordance with RECIST 1.1. For Phase Ib data the independent review will only be performed for subjects from cohorts with the RP2D.

The secondary efficacy endpoints will be analyzed using the FAS.

Overall response rate and best overall response

See definitions in [Section 2.5.2.1](#).

Duration of response

DOR only applies to subjects whose best overall response is CR or PR according to RECIST 1.1 based on local investigators or BIRC review of tumor assessment data. The start date is the date of first documented response of CR or PR (i.e., the start date of response, not the date when response was confirmed), and the end date is defined as the date of the first documented progression or death due to any cause. Subjects continuing without progression or death will be censored at the date of their last adequate tumor assessment using the censoring rule described for the PFS analysis.

Disease control rate

DCR is defined as the proportion of subjects with a BOR of CR or PR, or SD according to RECIST 1.1 criteria.

Time to response

TTR is the time from date of first administration of study treatment to first documented response of CR or PR (which must be confirmed subsequently) using local investigators or BIRC review of tumor assessment data and according to RECIST 1.1. Subjects who did not achieve a confirmed PR or CR will be censored at:

- the maximum follow-up time (i.e. FPFV – LPLV used for the analysis in the respective subject group) for subjects who had a PFS event (i.e. either progressed or died due to any cause); [REDACTED]
- the last adequate tumor assessment date for all other subjects

Progression-free survival

PFS is defined as the time from the date of first administration of study treatment to the date of the first documented progression or death due to any cause. PFS will be based on local investigators or BIRC review of tumor assessments and using RECIST 1.1 criteria (see [CSP Appendix 1]). PFS will be censored at the date of the last adequate tumor assessment if no PFS event is observed prior to the analysis cut-off date [REDACTED] or before the start of the new anti-cancer therapy date, whichever is earlier. (See Section 2.7.3 for additional details regarding censoring rules and determination of date of last adequate tumor assessment, see Section 2.5.2.1 regarding exceptions in determining anti-cancer therapy usage). Discontinuation due to disease progression (collected on the ‘End of treatment’ and ‘End of post treatment follow up’ disposition pages without supporting objective evidence satisfying progression criteria per RECIST 1.1 will not be considered disease progression for PFS derivation. Clinical deterioration will not be considered as a qualifying event for progression.

Overall survival

OS is defined as the time from date of first administration of study treatment to date of death due to any cause. All deaths occurring on or before the efficacy cut-off date will be used in the OS analysis. If a subject is not known to have died at the time of the analysis, the OS time will be censored at the date of last contact.

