2.7.2 Statistical hypothesis, model, and method of analysis

ORR, BOR, and DCR

ORR and DCR will be summarized using descriptive statistics (N, %) by treatment group (Phase Ib) or group (Phase II) along with two-sided exact binomial 95% CIs [Clopper and Pearson 1934]. As a supportive analysis ORR and DCR based on the BIRC review of tumor data will also be summarized. Frequencies of the BOR categories will also be presented. Subjects with ‘unknown’ BOR will be summarized by reason for having unknown status (see Section 2.5.2.4) based on both investigator and BIRC assessment. A concordance analysis of BOR (see Section 2.5.2.4) will be provided for Phase Ib (RP2D) and Phase II groups.

A listing will be presented with overall responses at all assessment timepoints, with percentage change from baseline, difference between NADIR and sum of diameters, and BOR per subject.

Waterfall plots based on both investigator and BIRC assessment will be prepared per treatment group.

Time to event endpoints

TTR, DOR, PFS and OS data will be listed and summarized by treatment group. The distribution of TTR, DOR, PFS, and OS, respectively, will be estimated using the Kaplan-Meier method. The results will be presented graphically. The median, 25th and 75th percentiles along with 95% CI will be presented along with the survival probabilities at 6, 9, 12, 18, and 24 months and their associated 95% CI.

These analyses will be based on both investigator and BIRC assessment.

Listings of TTR and DOR details as well as PFS and OS data by treatment group (Phase Ib) and Phase II group will be provided.

Censoring pattern of PFS

The number of subjects with a PFS event and the number of subjects censored for the PFS analysis will be summarized. In addition, a summary of reasons for PFS censoring will be provided by treatment group based on the following reasons:

1. Ongoing without event
2. Lost to follow-up
3. Withdrew consent
4. Adequate assessment no longer available
5. Initiation of new cancer therapy prior to progression
6. Event after ≥ 2 missing tumor assessments

The PFS censoring reasons are defined in the following way.

If the time interval between the last adequate tumor assessment (TA) date and the earliest of the following dates is less than or equal to the interval of 2 missing TAs (see [Section 2.7.3](#) for definition):

1. Analysis cut-off date
2. Start date of further anti-neoplastic therapy
3. Date of consent withdrawal

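### Time to response: some non-responders who can no longer respond are censored at their last scan, so the Kaplan-Meier response curve can exceed the ORR

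*SAP*

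**What the plan says.** SAP section 2.7.1 gives two TTR censoring rules for subjects without a confirmed response. The first sets the time to maximum follow-up "for subjects who had a PFS event (i.e. either progressed or died due to any cause". The second uses "the last adequate tumor assessment date for all other subjects". Section 2.7.2 adds: "The distribution of TTR, DOR, PFS, and OS, respectively, will be estimated using the Kaplan-Meier method". The output includes quartiles, the median and probabilities at 6, 9, 12, 18 and 24 months. The analysis set is the FAS.

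Three rules in sections 2.5.2.1 and 2.5.2.3 decide when response is no longer possible:

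- "For BOR only tumor assessments performed before the start of any new anti-cancer therapy (including medication, radiotherapy and surgery) will be considered" (permitted bone and CNS treatment excepted).
- "any assessments taken more than 30 days after the last dose of study treatment will not be included in the best overall response derivation".
- A PR needs "at least two determinations of PR or better at least 4 weeks apart before the end of treatment", and CR has a parallel requirement.

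For the ORR, also in the FAS, "Subjects with unknown or missing BOR will be counted as failures".

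Section 2.7.3 and Table 2-4 censor PFS, rather than count an event, when new therapy starts before documented progression, when progression is only clinical, and when the event follows two or more missed assessments. With no post-baseline assessment, the date of last adequate assessment becomes the treatment start date.

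**The concern.** The evident reason for the first TTR rule is that a subject who has progressed or died cannot respond any more, so removing that subject early would mislead. The SAP's response rules make the same true of a non-responder who has switched therapy or is more than 30 days past the last dose. Without a PFS event, that subject is nevertheless censored at the last adequate scan. Kaplan-Meier then treats the subject as someone who would have gone on to respond at the rate of those still at risk, which the SAP's definitions rule out.

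At stake is agreement between two results on the same subjects. The TTR curve and its 6- to 24-month probabilities could show more response than the ORR. The error runs in one direction only. It grows with the number who stop or switch without documented progression, so poorer tolerability could make TTR look better. The BIRC-based TTR may be more exposed: a subject taken off treatment for investigator-assessed progression that the BIRC does not confirm has no BIRC event and falls under the second rule.

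**Working it through.** The SAP states no figure on this point, so there is none to reproduce.

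**Inputs from the SAP.** The censoring and response rules above; N = 40, the minimum for Group 1 and for Group 3 (section 1.1.2). Sections 2.3.3 and 5.1.1 expect nobody to be on treatment at the final analysis, so most second-rule censorings would not be subjects still able to respond. Some subjects may have been ongoing at the separate efficacy cut-off.

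**Assumptions, not in the SAP.** Scans every 8 weeks. Responses at weeks 8/16/24 number 12/5/3 (20 of 40, ORR 50%) or 18/7/3 (28 of 40, ORR 70%). Of the non-responders, c = 2 to 8 can no longer respond and have no PFS event; the others have a PFS event and stay to maximum follow-up.

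**Formulas.** Let r be all responders and r₁ those at week 8. KM is the estimated probability of not yet having responded.

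- All c censored on day 1: 1−KM = r/(N−c).
- All c censored at week 8, after that week's responses: 1−KM = 1 − [(N−r₁)/N] × [(N−r−c)/(N−r₁−c)].
- All c kept to maximum follow-up: 1−KM = r/N = ORR.

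**Worked values.**

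- ORR 50%, c = 8, day 1: 20/32 = 62.5%.
- ORR 50%, c = 8, week 8: 1 − (28/40)(12/20) = 58.0%.
- ORR 70%, c = 2, week 8: 1 − (22/40)(10/20) = 72.5%.

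| c | ORR 50%, day 1 | ORR 50%, week 8 | ORR 70%, day 1 | ORR 70%, week 8 |
|---|---|---|---|---|
| 0 | 50.0 | 50.0 | 70.0 | 70.0 |
| 2 | 52.6 | 51.5 | 73.7 | 72.5 |
| 4 | 55.6 | 53.3 | 77.8 | 75.6 |
| 6 | 58.8 | 55.5 | 82.4 | 79.4 |
| 8 | 62.5 | 58.0 | 87.5 | 84.3 |

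Entries are the final 1−KM in percent. Week 24 is 168/30.4375 = 5.5 months, so in these scenarios every landmark from 6 months on carries the full excess.

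**When there is no excess.** If all c are censored at or after the last response (week 32, say), 1−KM equals the ORR exactly. Censoring passes a subject's weight to those still at risk, so the curve rises above the ORR only if one of those later responds. It cannot fall below it.

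**Median.** At an ORR of 70%, KM after week 8 is 22/40 = 0.55 with everyone kept in and 15/40 = 0.375 after week 16, so the median is week 16. With eight subjects censored on day 1, KM after week 8 is 14/32 = 0.4375 and the median moves to week 8. With two censored on day 1 it is 20/38 = 0.526 and the median stays at week 16.

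A median can also appear where fewer than half respond. Take 19 of 40 responders (12/5/2; 47.5%) and four such subjects, two censored on day 1 and two at week 8: 1 − (26/38)(19/24)(17/19) = 51.5%.

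**The case against.** **Choice of estimand.** Censoring at new therapy can be defended as a hypothetical strategy and matches how the SAP handles PFS. ORR and TTR would then answer different questions, and a gap between them would be no error. This would carry weight if TTR censored everyone that way. It does not: the first rule already treats subjects with a PFS event as never responding, and the second departs from that for subjects equally unable to respond.

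**Who is affected.** The gloss on PFS event in section 2.7.1 could be read to include progression or death after a switch, which would put those subjects under the first rule. Section 2.7.3 and Table 2-4 point the other way, but the wording is ambiguous. Subjects who switch or stop without ever progressing are affected on either reading. Text after the first rule is blacked out; the second rule is intact and covers everyone else.

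**Size.** Eight of 40 is the upper end of an assumed range. The day-1 column also needs every such subject to lack a post-baseline scan and a PFS event. That caution stands.

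**Losses and withdrawals.** For a subject whose response was simply not observed, ordinary censoring is defensible. That also stands, and the fix respects it.

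**Stronger readings.** A reader might infer that the curve must exceed the ORR, or that the median TTR is always too short. The SAP gives neither counts nor timing, and both depend on them. A reader might also take the maximum follow-up, written as FPFV – LPLV, for a negative duration; the dash can equally denote a span, and nothing here rests on it.

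**Conclusion.** The inconsistency is real and follows from the SAP's own rules. Among non-responders who can no longer respond, those with a PFS event stay at risk and those without one are removed. Whenever one of the latter is censored before a later response in the group, 1−KM for TTR exceeds the ORR; otherwise the two are equal.

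Under the stated assumptions the excess is about 1.5 to 12.5 points at an ORR of 50% and 2.5 to 17.5 points at 70%. Quartiles and the median shift only in some configurations. The actual size depends on how many such subjects there are and when they are censored, which the SAP does not say. TTR is a secondary, descriptive endpoint without a test, and the ORR itself is unaffected. The point still merits correction, because the report could otherwise show two response figures that disagree for the same subjects.

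**What to change.** Extend the first TTR rule in section 2.7.1. Alongside those with a PFS event, censor at maximum follow-up every non-responder who started new anti-cancer therapy (with the existing bone and CNS exceptions), or whose study treatment ended more than 30 days before the efficacy cut-off. Alternatively, estimate cumulative incidence with these as competing events; it reaches the same plateau.

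Keep censoring at the last adequate assessment for two kinds of subject: those still able to respond at the efficacy cut-off, and those lost to follow-up or withdrawing consent whose response was not observed. State that this second category takes precedence when loss or withdrawal is what ended the assessments. Add a sensitivity analysis that treats that category as non-responders. Apply the same rules to investigator and BIRC assessments.

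The cost is one reworded SAP rule, a small programming change and one extra sensitivity output. The downside is that TTR percentiles and landmark rates may become slightly less favourable.
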